Rationale for Using NRT in the Treatment Protocol. Because clinical guidelines recommend that all smokers attempting to quit receive pharmacotherapy, we believe it is important to include pharmacotherapy (NRT) as part of our smoking cessation treatment. We chose to provide the patch for 8 weeks because longer than 8 weeks does not appear to improve treatment efficacy³. We chose the Nicoderm CQ®, 24-hour transdermal nicotine patches (TNP) as part of the study because of the extensive empirical literature supporting its effectiveness and safety, its ease of use, and its relatively benign side effect profile that have led to its approval as an over-the-counter medication³⁷.

Rationale for Using a 3-month Follow-Up. We considered using a longer follow-up period (e.g., 6- and 12-month), but 3-month follow-up seems reasonable given the well-accepted finding that most relapses have occurred by 3 months, with only minor changes occurring thereafter³⁸⁻⁴⁰. Using the shorter-term follow-up is also reasonable given the shorter funding period for the R34 mechanism.

C3. Study Participants

We plan to recruit 100 male and female participants between the ages of 18 and 65. Inclusion criteria are: (1) daily smoker for at least one year, smoking an average of at least 10 cigarettes per day, and motivated to quit smoking (> 5 on a 10-point scale). Exclusion criteria are (1) use of other tobacco products (including e-cigarettes); (2) psychiatric conditions that are contraindications to the use of any treatment option in the protocol (e.g., currently suicidal or high suicide risk, current or past psychotic disorders of any type, bipolar disorder, schizophrenia or schizoaffective disorder, anorexia, bulimia, alcohol or substance disorder within the last 6 months); (3) current use of any pharmacotherapy or psychotherapy for smoking cessation not provided by the researchers during the quit attempt; and (4) insufficient command of the English language.

C3b. Recruitment and Timeline

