As in past an ongoing work⁴³⁻⁴⁶, self-reported smoking status will be assessed during the intervention (weeks 0-7), at posttreatment (week 8), and at 1-month (week 9), 2-month (week 13) and 3-month (week 17) follow-up (i.e., post-quit; see Figure 6). Self-reported abstinence will be verified by expired carbon monoxide (CO). Abstinence at the 2-month (week 13) and 3-month (week 17) follow-up will additionally be verified with saliva cotinine. We will use the timeline follow-back (TLFB) procedure at all assessments to assess cigarette consumption at each day following the previous assessment, which has demonstrated good reliability and validity⁴⁹. Self-reported abstinence will be overridden by a positive carbon monoxide ($\geq 4\text{ppm}$)⁵⁰ or saliva cotinine verification ($>10 \text{ ng/mL}$)⁵¹. If neither CO nor cotinine levels are available to verify abstinence at an assessment, abstinence will be considered missing data⁵². We will employ 7-day point prevalence abstinence (PPA) and prolonged abstinence (PA) as the primary outcomes. PPA will be defined as no smoking, not even a puff, in the 7 days prior to any assessment. Failure to maintain PA at any assessment will be defined by smoking on 7 consecutive days or smoking at least once each week over 2 consecutive weeks⁴⁰.

Figure 6. Assessment Schedule

| | Protocol Weeks | | | | | | |
|--|----------------|----------|----------|-----------|------------------|---------------|-------------------------------|
| | -3,-2,-1 | 0 | 1-4 | 5 | 6 | 8 | 9-17 |
| | End Points | | | | | | |
| | Pre-Screen | Baseline | Pre-Quit | Quit Week | 1-Week Follow-up | Posttreatment | 1-, 2-, and 3-Month Follow-up |
| Screening | | | | | | | |
| Demographics | X | | | | | | |
| Smoking history | X | | | | | | |
| Motivation to quit | X | | | | | | |
| Nicotine dependence (FTND) | X | | | | | | |
| Psychiatric diagnosis and suicide (MINI) | X | | | | | | |
| AIM 1: Efficacy | | | | | | | |
| Self-reported smoking (TLFB) | | X | X | X | X | X | X |
| Carbon monoxide | | X | X | X | X | X | X |
| Saliva cotinine | | | | | | | X ¹ |
| AIM 2: Mechanisms of Action | | | | | | | |
| Craving (QSU-B) | | X | X | X | X | | |
| Approach Bias (AAT; session data) | | X | X | X | | | |

¹ Only assessed at 2- and 3-month follow-up

C5c. Mechanisms of Action

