As per our pre-registered analysis plan ([name] et al., 2019), we examined the equivalence of the treatment groups on demographic and key psychological variables prior to treatment; variables on which the groups differed were included as covariates in the final analyses if they were significantly related to outcome. The only variable that differed between groups was the initial avoidance tendency score ($t(94) = 2.88$, $p = 0.005$), which was added as a covariate in all analyses. A priori power analysis indicated greater than 0.80 power to detect a significant condition effect if the abstinence rate in ST+ABR was 42 % or greater (effect size $\omega = .238$) with a sample size of 100 (see [name] et al., 2019 for more details).

PROTECTION OF HUMAN SUBJECTS

Risks to Subjects

Human Subjects Involvement and Characteristics

We plan to enroll 100 participants total. The participant population will be comprised of both males and females of mixed ethnic and socioeconomic backgrounds. All participants meeting entrance criteria will be offered the opportunity to participate. Participants will not be excluded on the basis of gender or race. Inclusion and exclusion criteria are presented in the Figure 7.

Figure 7. Study Entry Criteria

| Inclusion Criteria | |
|-------------------------------|---|
| 18 to 65 years old | |
| Informed consent | The capability and willingness to give written informed consent, to understand inclusion and exclusion criteria, and to accept the randomized group assignment are required. |
| Daily smoker | Smoking status will be assessed via self-report at screening. Only participants who currently smoke ≥ 10 cigarettes per day can be eligible. |
| Motivated to quit | Reporting motivation to quit smoking (>5 on a 0-10 scale). |
| Exclusion Criteria | |
| Use of other tobacco products | Use of tobacco products, including e-cigarettes, will be assessed during screening. |
| Psychiatric disorders | Currently suicidal or high suicide risk, current or past psychotic disorders of any type, bipolar disorder (I, II, or NOS), schizophrenia or schizoaffective disorder, anorexia, bulimia, alcohol or substance dependence within the last 6 months, patients with comorbid psychiatric conditions that are relative or absolute contraindications to the use of any treatment option in the protocol. These will be assessed by the MINI. |

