| Current treatment | Current use of any pharmacotherapy or psychotherapy for smoking cessation not provided by the researchers during the quit attempt. Current use of psychotropic medication. Here, although subjects will be excluded at intake for use of psychotropic medications and asked not to initiate pharmacotherapy during the study period, we believe it would be unethical to prevent them from starting these medications once the study has begun. Thus, we will assess for the initiation of psychotropic medications throughout treatment and utilize this information when analyzing the study results. Concurrent psychotherapy initiated within three months of baseline, or ongoing psychotherapy of any duration directed specifically toward the treatment of anxiety or mood disorder other than general supportive therapy initiated at least 3 months prior to the study. |
| Other exclusions | Insufficient command of the English language (i.e., they cannot carry on a conversation with an interviewer in the English language or read associated text). |

Sources of Research Material

Research material will consist of patient treatment history, symptom and functioning assessments, records of treatment sessions and demographic information collected during the study for research purposes. All research materials are similar to what is commonly collected in routine clinical practice. The specific patient assessment and self-report questionnaires that will be utilized in this study are as follows: Mini International Neuropsychiatric Interview (MINI), The Fagerström Test for Nicotine Dependence (FTND), Smoking History Questionnaire, Saliva cotinine, Carbon monoxide analysis of breath samples, Smoking Urges-Brief (QSU-B) and the Approach-Avoidance Task (AAT).

Potential Risks

Human subject risk related to the assessment and intervention procedures are small. Potential risks include nicotine patch side effects. More common side effects include local skin irritation at the site of the patch, nausea if the dose is too large or if the patient continues to smoke at a high level while using the patch, and disturbed and vivid dreams. Less common are allergic skin reactions. Other potential risks include withdrawal symptoms after quitting as well as breach of confidentiality. Below, we detail how we will guard against each of these potential risks. No known risks are associated with the other interventions.

Protection of Human Subjects from Research Risk

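### Non-combusted nicotine use is not recorded after screening, so adding cotinine at weeks 13 and 17 can turn an abstinent PPA score into a non-abstinent one with no change in behaviour

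*Combined protocol and SAP*

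**What the plan says.** **Product use.** Section C3 excludes users of other tobacco, e-cigarettes included. Figure 7 says when this is checked: "Use of tobacco products, including e-cigarettes, will be assessed during screening". Neither Figure 6 nor the instrument list under Sources of Research Material shows a measure of other nicotine products, or of patch use, after entry.

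**Self-report.** Under C5b the timeline follow-back (TLFB) is used at all assessments "to assess cigarette consumption at each day following the previous assessment". No other product is named.

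**Verification.** CO is taken at every assessment. In addition, "Abstinence at the 2-month (week 13) and 3-month (week 17) follow-up will additionally be verified with saliva cotinine"; the Figure 6 footnote agrees: "Only assessed at 2- and 3-month follow-up". The rule begins "Self-reported abstinence will be overridden by a positive carbon monoxide" (4 ppm or more) and goes on to give saliva cotinine above 10 ng/mL the same force. It makes no exception for nicotine from another source. Abstinence is missing only when both biomarkers are absent.

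**Outcomes.** PPA requires that the participant has not smoked at all in the past 7 days. PA is lost by a run of seven smoking days, or by some smoking in each of two weeks in a row. Neither definition mentions e-cigarettes or smokeless products.

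**Analysis.** C8 models PPA and PA jointly, with treatment as a moderator of the post-quit slope. Aim 1A predicts a smaller decline under ST+ABR.

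**The concern.** The plan does not say whether a non-combusted nicotine product counts against abstinence, yet the biomarker schedule answers the question differently by visit. Through week 9 the test responds to smoke; from week 13 it also responds to nicotine. A participant whose behaviour is constant can then appear to relapse because the test changed. That change coincides with study time inside the post-quit segment, so it feeds a slope on which the trial has a stated hypothesis. With no record of product use, the analyst cannot say whether a cotinine override reflects cigarettes, the study patch or another product. The trial is meant to supply effect sizes for a larger follow-up study, so an unresolved definition would carry forward.

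**Working it through.** **Step 1. Score one unchanged participant visit by visit.** Take someone who smokes no cigarettes after the quit week but uses a non-combusted nicotine product. Assume CO below 4 ppm and, where sampled, cotinine above 10 ng/mL. That CO misses such products and cotinine detects their nicotine is general knowledge, not a statement in the documents.

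| Visit | TLFB | Biomarkers | Other nicotine recorded? | PPA as written |
|---|---|---|---|---|
| Weeks 6, 7, 8, 9 | 0 cigarettes | CO negative | No | Abstinent |
| Week 13 | 0 cigarettes | CO negative, cotinine positive | No | Overridden to non-abstinent |
| Week 17 | 0 cigarettes | CO negative, cotinine positive | No | Overridden to non-abstinent |

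**Step 2. Separate this from the study patch.** The planned course is 6 + 1 + 1 = 8 weeks from week 5, and 5 + 8 = 13. It ends at about the week 13 sample, so a positive cotinine there may come from the patch. On the planned course, week 17 is free of this.

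**Step 3. Locate it in the model.** C5b numbers the visits 0 to 17 and C8 numbers the weeks 1 to 18. On either numbering weeks 9, 13 and 17 lie in the post-quit segment, so the change of test falls within the modelled slope.

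**Step 4. Illustrate the size.** The documents give no switching rate and no figure for this effect. The power statement in C8 supplies plausible rates: 42% in ST+ABR with effect size .238. A control rate of 20% reproduces that effect size:

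(0.42 − 0.20) / (2 × √(0.31 × 0.69)) = 0.238.

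The power claim itself plays no part here. Assumptions: 50 per arm, true cigarette abstinence constant at 42% and 20%, and a share s of abstainers using such a product, all with positive cotinine. The rate at a cotinine visit is p(1 − s), the number recoded per arm is 50ps, and the drop is logit(p) − logit(p(1 − s)). With s equal in both arms:

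| s | ST+ABR | ST+CTRL | Recoded (ABR + CTRL) | Logit drop ABR | Logit drop CTRL | Difference in drop |
|---|---|---|---|---|---|---|
| 5% | 39.9% | 19.0% | 1.05 + 0.5 = 1.55 | 0.087 | 0.064 | 0.023 |
| 10% | 37.8% | 18.0% | 2.1 + 1.0 = 3.1 | 0.175 | 0.130 | 0.045 |
| 20% | 33.6% | 16.0% | 4.2 + 2.0 = 6.2 | 0.358 | 0.272 | 0.086 |
| 30% | 29.4% | 14.0% | 6.3 + 3.0 = 9.3 | 0.553 | 0.429 | 0.124 |

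At s = 10% in ST+ABR: ln(0.42/0.58) − ln(0.378/0.622) = −0.323 + 0.498 = 0.175.

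**Step 5. Unequal use, as a range only.** If only one arm switches, the log odds ratio at the cotinine visits moves by −0.175 (10%, ST+ABR only) or +0.130 (10%, ST+CTRL only). At 20% these become −0.358 and +0.272.

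**Step 6. Put it on a scale.** The standard error of a single-visit log odds ratio at 42% and 20% with 50 per arm is √(1/21 + 1/29 + 1/10 + 1/40) = √0.207 = 0.455. Equal switching at 10% to 20% moves the contrast by 0.10 to 0.19 standard errors (0.045/0.455 and 0.086/0.455). The largest one-arm case is 0.358/0.455 = 0.79. These are single-visit figures for PPA, not estimates from the joint mixed model.

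**The case against.** Much of the opposing case stands, and it limits the point.

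- **Not every product switch is affected.** A reader might infer that any move to other tobacco is misclassified. Burned products raise CO, can be caught at any visit, and fall under the plain meaning of smoking.
- **The flip is conditional.** It needs a cotinine sample above 10 ng/mL. A nicotine-free device or light use may stay below, and with no cotinine sample a negative CO can verify abstinence.
- **A fall between weeks 9 and 13 cannot be attributed to switching.** The patch course ends at about week 13.
- **PA may not move.** Zero recorded cigarettes with one positive cotinine does not plainly meet the PA failure rule, and C5b does not say how cotinine enters PA. Since C8 models PPA and PA jointly, the figures above do not carry over to the combined outcome.
- **A bias between arms is not shown.** A reader might infer that ABR, by training avoidance of smoking images, makes switching unequal. The documents offer no evidence of this: both arms receive the same CBT and patch and a plausible training rationale, and the trial is described as double-blind. Users of other products are also excluded at entry.
- **The problem is not invisible.** TLFB, CO and cotinine are all planned at weeks 13 and 17, so discordant records can be counted, although the source of the nicotine remains unknown.
- **C5b need not treat e-cigarette use as failure.** The stated endpoint is no smoking, and a cigarettes-only endpoint with a cotinine exception is equally coherent.

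None of this removes the core. Followed as written, the override rule scores the same behaviour differently at different visits.

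**Conclusion.** The concern holds for e-cigarettes and other non-combusted nicotine products, and for PPA. Such use is not recorded after screening, and verification changes from CO alone to CO plus cotinine with no rule for another nicotine source. Coded abstinence can therefore decline through the change of test alone. Week 17 is the clean instance, week 13 is confounded with the patch, and the effect on PA cannot be determined from the text.

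The size rests wholly on assumption. With 10% to 20% of abstainers using such a product, about 3 to 6 of 100 participants are recoded. The apparent decline is 0.18 to 0.36 logits in ST+ABR and 0.13 to 0.27 in ST+CTRL, and with equal use the arm contrast moves by only about 0.05 to 0.09. The distortion is thus mainly to the level of late abstinence and the overall slope. A material effect on the treatment comparison would need unequal use, which nothing in the documents establishes.

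**What to change.** 1. **Record.** In C5b and Figure 6, extend the TLFB at every post-quit visit through week 17 to e-cigarettes, other tobacco, non-study nicotine replacement and the study patch.
2. **Define.** State one rule, identical at every visit, for how non-combusted nicotine use counts towards PPA and PA. Two choices are coherent: count any e-cigarette or other tobacco use as non-abstinent throughout, or keep a smoking-only endpoint throughout. Either way, say how a positive cotinine is scored when a non-cigarette nicotine source is on record (under the first choice this still matters for the patch and non-study replacement), and whether cotinine can cause PA failure.
3. **Test sensitivity.** Repeat the main model with weeks 13 and 17 verified by CO only, so that one test applies at every visit. Report by arm and visit the number of records with zero cigarettes, negative CO and positive cotinine. Some of these may be cigarette use that CO missed, so the CO-only result shows how far the cotinine override matters rather than replacing the main analysis.

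The cost is a few questionnaire items and one scoring paragraph. The downside is reliance on self-report of other products, so unreported use would still flip. C8 is written in the past tense and reports a baseline test with 94 degrees of freedom, so data collection may have ended. In that case item 1 is no longer available and belongs in the follow-up trial, but item 3 needs no new data.

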We have a history of successful recruitment for NIH-funded trials of smoking cessation interventions and will use the approach that has been effective in these studies. Specifically, we will advertise through numerous community organizations that promote quit smoking initiatives and also use social media and Internet outlets to advertise our study. The greater Austin, TX area has a population of 1.9 million. The enrollment period will be 127 weeks (of 156 weeks), allowing sufficient time for start-up activities (12 weeks) and participants to complete the study protocol (17 weeks) and complete data analysis (starting at week 139). Accordingly, we need to enroll 0.8 patients every week or 4 patients every 5 weeks. Currently, we screen, on average, 22.45 individuals weekly (or 112 every five weeks) for ongoing smoking cessation studies. Given the required conversion rate is 4% (4 of 112), we deem this targeted enrollment feasible.

C3c. Screening Procedures

An initial web screen will be performed with all potential participants to determine initial eligibility (e.g., smoking history, motivation to quit). A UT staff member will contact potential participants who appear eligible following screen to provide more details about the study and, if the participant provides informed consent, the staff member will conduct the Mini International Neuropsychiatric Interview (MINI)^{41,42} to assess psychiatric exclusion criteria. Participants who are eligible and remain interested will be enrolled.

C4. Procedures

C4a. Randomization and Baseline Visit

Eligible participants will be randomized to study condition prior to the baseline visit. The project biostatistician, [name], will oversee the randomization. He will use variable-sized permuted block-randomization (block sizes will vary from 4 to 12). Prior to data analyses, [name] will check the balance of randomization and control for any factors that are imbalanced. The baseline visit serves to obtain initial assessments on the outcome and mechanisms variables.

C4b. Interventions

Participants will receive a standard, individual smoking cessation treatment based on the most recent clinical practice guideline from the U.S. Department of Health and Human Services, Treating Tobacco Use and Dependence³. Consistent with the manualized procedures we have employed in past and ongoing NIDA-funded investigations⁴³⁻⁴⁶, the standard intervention (ST) involves a combination of CBT plus NRT.

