We will use the Questionnaire of Smoking Urges-Brief (QSU-B⁵³), which is a psychometrically sound measure of craving. We will administer the AAT^{14,18,22} in order to assess approach bias at baseline. The ATT instructs participants to pull a joystick upon seeing an image tilted to the right and to push the joystick upon seeing a left-tilt image, while ignoring the image content (i.e., indirect instructions). By pulling the joystick (approach), the picture grows in size; by pushing the joystick away (avoidance), the picture shrinks. The AAT includes 96 trials in which each of 24 smoking-related pictures (e.g., woman lighting a cigarette) and each of 24 positive images (e.g., group of friends exercising) will be pulled and pushed. An approach bias score for smoking-related pictures will be computed for each participant by subtracting the average time it takes to pull smoking-related images from the average time it takes to push away these images. Thus, a positive value indicates an approach tendency toward smoking stimuli, whereas a negative value is indicative of avoidance of smoking images. As discussed in section C4a, the ABR also involves 12 incompatible smoking-related trials in the last half of each training session, allowing us to compute the approach bias at the end of each of the seven training sessions in ABR^{11,14}. Specifically, the approach bias score will be computed by subtracting the average time it takes to pull smoking-related images (the 12 incompatible trials in the second half of each session) from the average time it takes to push smoking-related images (48 trials). Similarly, we will compute an approach bias score for the end of each of seven CTRL training sessions by subtracting the average time it takes to pull smoking-related images (the 24 incompatible trials in the second half of each session) from the average time it takes to push smoking-related images (the 24 compatible trials in the second half of each session)^{11,14}. Finally, we will explore scoring algorithms for the AAT and session data that standardize the bias scores by dividing an individual's difference in response times by a personalized standard deviation of these response latencies. A similar scoring approach has been used successfully for a related task, the Implicit Association Test (IAT⁵⁴).

C6. Training and Quality Assurance/Quality Control

C6a. Checks of Integrity of Screening Procedures

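### Covariates are picked by screening the trial's own data, and FTND, measured before randomisation, is not in the abstinence model: a cheap improvement is available

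*Combined protocol and SAP*

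**What the plan says.** - **C8, the rule.** The arms are compared on demographic and psychological measures "prior to treatment; variables on which the groups differed were included as covariates in the final analyses if they were significantly related to outcome". A variable must therefore pass two conditions: imbalance and relation to outcome. C8 says this follows a pre-registered plan. It lists no variables and gives no threshold.
- **C8, the result.** "The only variable that differed between groups was the initial avoidance tendency score". The reported test statistic is 2.88 on 94 degrees of freedom, with a p-value of 0.005. On its use, C8 says of this score only: "which was added as a covariate in all analyses". The relation of the score to outcome, the direction of the gap and the abstinence result without the score are not given.
- **C4a.** The biostatistician "will check the balance of randomization and control for any factors that are imbalanced". This is one condition only.
- **FTND.** C5a and Figure 6 place it at pre-screening, and C4a randomises eligible participants after that and before the baseline visit. A4 describes nicotine dependence as related to cessation outcomes, without naming FTND or giving a strength. Specific Aim 2C and C5a give it a moderator role. C8's abstinence model lets treatment group modify the jump at quitting and the post-quit slope; it names no FTND term.
- **Avoidance score.** C5c gives the AAT "in order to assess approach bias at baseline". C8 does not define the initial avoidance tendency score.

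**The concern.** Under randomisation, whether a baseline variable happens to be imbalanced says nothing about whether it predicts outcome. A rule that starts from observed imbalance therefore picks covariates largely by chance and usually leaves out the ones worth adjusting for. FTND is an obvious candidate: it is already collected, it precedes allocation, and the protocol itself links the construct to cessation.

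At stake is some power in the abstinence comparison of a pilot meant to supply effect-size data for a larger trial. A second, separate matter is that the one covariate actually used is reported against only half of C8's rule, so a reader cannot see whether the rule was met or how far the abstinence result depends on that covariate.

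**Working it through.** **1. The plan's own figures.**
- Balance test: t = 2.88 on 94 df gives two-sided p = 0.0049, which agrees with 0.005. In a two-sample t test, 94 df means 96 participants with a score, so up to 4 lack it if the planned 100 were randomised.
- Size of the gap, assuming near-equal arms: d = 2t/√N = 2 × 2.88/√96 = 0.588. SE = √(4/96 + 0.588²/(2 × 96)) = 0.209. The 95% CI is 0.18 to 1.00. A 40/56 split gives 0.596.
- Control rate implied by C8's effect size of .238 and 42%: (0.42 − 0.20)/2 ÷ √(0.31 × 0.69) = 0.11/0.4625 = 0.238, so 20%.
- Power at one time point, N = 100, two-sided 5% (assumed): noncentrality 100 × 0.238² = 5.66, power 0.663. C8 states more than 0.80, but its alpha, control rate and within-person correlation are not given and its model uses repeated measures. The 0.66 serves here only as a reference level.

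**2. What the two screens do.** Simulated trials: 50 per arm, marginal rates 20% vs 42%, ten independent normal baseline variables of which one is prognostic, 5% screens, Wald test, 10,000 trials per cell. The odds ratios per SD are assumptions.

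| OR per SD | Enters, C4a rule | Enters, C8 rule | Power, C4a rule | Power, C8 rule | Power, fixed covariate |
|---|---|---|---|---|---|
| 1 (not prognostic) | – | – | 0.647 | 0.649 | 0.660 |
| 1.5 | 5.5% | 2.2% | 0.656 | 0.656 | 0.684 |
| 2 | 5.1% | 4.1% | 0.654 | 0.657 | 0.710 |
| 3 | 5.2% | 5.0% | 0.658 | 0.658 | 0.748 |

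The prognostic variable is thus left out in about 95% of trials (up to 98% under the C8 rule at 1.5). Repeat runs gave 0.67-0.68, 0.69-0.70 and 0.75 for the fixed covariate. With no treatment effect, rejection rates were 0.042-0.045 under either rule and 0.046-0.051 with the fixed covariate.

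**3. What kind of gain this is.** In the same single-time-point setting (6,000 runs), the group log odds ratio and its standard error were as follows.

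| Model | Mean log OR | Mean SE | Ratio |
|---|---|---|---|
| Unadjusted | 1.10 | 0.467 | 2.36 |
| Adjusted, OR 1.5 | 1.15 | 0.482 | 2.39 |
| Adjusted, OR 2 | 1.22 | 0.500 | 2.44 |
| Adjusted, OR 3 | 1.37 | 0.537 | 2.55 |

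The standard error rises. Power improves because the adjusted model targets a larger, conditional odds ratio. A standardised risk difference does become 2-9% less variable. This comparison was not made in the GLMM.

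**4. A model shaped like C8's.** Random-intercept logistic model, one outcome, 12 visits, person SD 2, 3% abstinent pre-quit (all assumed), 50 per arm. Power for group-by-jump:
- No group main effect, 20% vs 33%, 640 runs: 0.72, 0.69, 0.70 without the covariate and 0.74, 0.73, 0.80 with it, at odds ratios 1.5, 2, 3.
- Group main effect included, 20% vs 42%, 400 runs: 0.692 to 0.695 at odds ratio 2, and 0.645 to 0.658 at 3.

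The documents do not say which form was fitted. Neither version is the bivariate PPA/PA model.

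**The case against.** The strongest reply is that adding FTND is an efficiency preference, not the correction of an error. C8's rule is said to be pre-registered. A4 does not name FTND, and the reference it cites is titled on time to first cigarette. Entry requires at least 10 cigarettes a day, which may narrow the range of dependence. A model that tests group as a moderator would ordinarily contain a group main effect, and then the gain on the jump term is 0-1 point. FTND also has a planned use as a moderator. Finally, only one variable differed between the arms, so the conflict between C4a and C8 matters here only for whether that score should enter. All of this stands, and it limits the point to a cheap improvement.

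Three stronger readings are tempting, and the documents support none of them:
- *The screens inflate type I error.* The simulated rates stay at or below 5%.
- *The avoidance score is a session-1 training score, so adjusting for it removes part of the training effect.* C8 uses the same term for scores over the training weeks, which invites this. But its balance check is on variables measured before treatment, C4a says "The baseline visit serves to obtain initial assessments on the outcome and mechanisms variables", and C5c provides a baseline AAT. On that reading training cannot have changed the score, and adjustment handles a chance imbalance.
- *The score was entered against the rule, or the power statement is wrong.* Its relation to outcome is unreported, which is not the same as absent. The inputs to the power statement are not all given.

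**Conclusion.** The point holds as a cheap improvement. Both covariate rules depend on the trial's own data, and either would leave out a prognostic baseline variable in about 95% of trials. FTND, available before allocation, is not a named term in the abstinence model. At one time point the cost is about 1-2, 3-5 or 9 points of power at odds ratios per SD of 1.5, 2 or 3. There is little or no cost if FTND is not prognostic, and almost none on the jump term if a group main effect is fitted. These sizes rest on an assumed FTND strength, a 5% screen, 50 per arm and 20% vs 42%. The benefit is power for a conditional effect; it should not be described as a smaller standard error of the log odds ratio.

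The missing outcome relation for the avoidance score, and the missing result without it, are reporting gaps that do not depend on any simulation. How far the score moves the jump and slope terms cannot be known from the documents.

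**What to change.** Keep the registered model as the main result. Beside it, labelled post hoc because C8 already reports results, give:
1. The abstinence GLMM with FTND as a fixed covariate, whatever its balance or p-value.
2. The abstinence GLMM without the avoidance score, keeping participants who lack the score, with the number analysed in each model.

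State that the adjusted odds ratio is conditional and larger than the unadjusted one, or also report a standardised risk difference when passing effect-size data to the larger trial.

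As minor clarifications: use one covariate rule in C4a and C8, report whether the score was related to outcome, and confirm that it is the week-0 AAT.

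The cost is SAP wording and re-runs of one existing model on data already collected. The downsides are one extra parameter (against about 50 × 0.20 + 50 × 0.42 = 31 abstainers at one time point), the post hoc label, and possibly no gain.
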